5.3.5.13 Patient-Reported Outcome Data

Adverse event reports will not be derived from PRO data by the Sponsor, and safety analyses will not be performed using PRO data. However, if any PRO responses suggestive of a possible adverse event are identified during site review of the PRO data, the investigator will determine whether the criteria for an adverse event have been met and, if so, will report the event on the Adverse Event eCRF.

5.4 IMMEDIATE REPORTING REQUIREMENTS FROM INVESTIGATOR TO SPONSOR

Certain events require immediate reporting to allow the Sponsor to take appropriate measures to address potential new risks in a clinical trial. The investigator must report such events to the Sponsor immediately; under no circumstances should reporting take place more than 24 hours after the investigator learns of the event. The following is a list of events that the investigator must report to the Sponsor within 24 hours after learning of the event, regardless of relationship to study drug:

- Serious adverse events (defined in Section 5.2.2; see Section 5.4.2 for details on reporting requirements)
- Adverse events of special interest (defined in Section 5.2.3; see Section 5.4.2 for details on reporting requirements)
- Pregnancies (see Section 5.4.3 for details on reporting requirements)

The investigator must report new significant follow-up information for these events to the Sponsor immediately (i.e., no more than 24 hours after becoming aware of the information). New significant information includes the following:

- New signs or symptoms or a change in the diagnosis
- Significant new diagnostic test results
- Change in causality based on new information
- Change in the event's outcome, including recovery
- Additional narrative information on the clinical course of the event

Investigators must also comply with local requirements for reporting serious adverse events to the local health authority and IRB/EC.

5.4.2 Reporting Requirements for Serious Adverse Events and Adverse Events of Special Interest

5.4.2.1 Events That Occur prior to Study Drug Initiation

After informed consent has been obtained but prior to initiation of study drug, only serious adverse events caused by a protocol-mandated intervention should be reported. The paper Clinical Trial Serious Adverse Event/Adverse Event of Special Interest Reporting Form provided to investigators should be completed and submitted to the Sponsor or its designee immediately (i.e., no more than 24 hours after learning of the event), either by faxing or by scanning and emailing the form using the fax number or email address provided to investigators.

5.4.2.2 Events That Occur after Study Drug Initiation

After initiation of study drug, all adverse events will be reported until 30 days after the last dose of study drug and until 90 days for serious adverse events or adverse events of special interest. Investigators should record all case details that can be gathered immediately (i.e., within 24 hours after learning of the event) on the Adverse Event eCRF and submit the report via the electronic data capture (EDC) system. A report will be generated and sent to Roche Safety Risk Management by the EDC system.

In the event that the EDC system is unavailable, the paper Clinical Trial Serious Adverse Event/Adverse Event of Special Interest Reporting Form provided to investigators should be completed and submitted to the Sponsor or its designee immediately (i.e., no more than 24 hours after learning of the event), either by faxing or by scanning and emailing the form using the fax number or email address provided to investigators. Once the EDC system is available, all information will need to be entered and submitted via the EDC system.

Instructions for reporting serious adverse events that occur > 30 days after the last dose of study treatment are provided in Section [5.6](#).

5.4.3 Reporting Requirements for Pregnancies

5.4.3.1 Pregnancies in Female Patients

Female patients of childbearing potential will be instructed through the Informed Consent Form to immediately inform the investigator if they become pregnant during the study or within 5 months after the last dose of study drug. A Clinical Trial Pregnancy Reporting Form should be completed and submitted to the Sponsor or its designee immediately (i.e., no more than 24 hours after learning of the pregnancy), either by faxing or by scanning and emailing the form using the fax number or email address provided to investigators. Pregnancy should not be recorded on the Adverse Event eCRF. The investigator should discontinue study drug and counsel the patient, discussing the risks of the pregnancy and the possible effects on the fetus. Monitoring of the patient should continue until conclusion of the pregnancy. Any serious adverse events associated with the pregnancy (e.g., an event in the fetus, an event in the mother during or after the pregnancy, or a congenital anomaly/birth defect in the child) should be reported on the Adverse Event eCRF. In addition, the investigator will submit a Clinical Trial Pregnancy Reporting Form when updated information on the course and outcome of the pregnancy becomes available.

5.4.3.2 Abortions

A spontaneous abortion should be classified as a serious adverse event (as the Sponsor considers abortions to be medically significant), recorded on the Adverse Event eCRF, and reported to the Sponsor immediately (i.e., no more than 24 hours after learning of the event; see Section [5.4.2](#)).

If a therapeutic or elective abortion was performed because of an underlying maternal or embryofetal toxicity, the toxicity should be classified as a serious adverse event, recorded on the Adverse Event eCRF, and reported to the Sponsor immediately (i.e., no more than 24 hours after learning of the event; see Section [5.4.2](#)). A therapeutic or elective abortion performed for reasons other than an underlying maternal or embryofetal toxicity is not considered an adverse event.

All abortions should be reported as pregnancy outcomes on the paper Clinical Trial Pregnancy Reporting Form.

5.4.3.3 Congenital Anomalies/Birth Defects

Any congenital anomaly/birth defect in a child born to a female patient exposed to study treatment or the female partner of a male patient exposed to study treatment should be classified as a serious adverse event, recorded on the Adverse Event eCRF, and reported to the Sponsor immediately (i.e., no more than 24 hours after learning of the event; see Section [5.4.2](#)).

5.5 FOLLOW-UP OF PATIENTS AFTER ADVERSE EVENTS

5.5.1 Investigator Follow-Up

The investigator should follow each adverse event until the event has resolved to baseline grade or better, the event is assessed as stable by the investigator, the patient is lost to follow-up, or the patient withdraws consent. Every effort should be made to follow all serious adverse events considered to be related to study drug or trial-related procedures until a final outcome can be reported.

During the study period, resolution of adverse events (with dates) should be documented on the Adverse Event eCRF and in the patient's medical record to facilitate source data verification.

All pregnancies reported during the study should be followed until pregnancy outcome.

5.5.2 Sponsor Follow-Up

For serious adverse events, adverse events of special interest, and pregnancies, the Sponsor or a designee may follow up by telephone, fax, electronic mail, and/or a monitoring visit to obtain additional case details and outcome information (e.g., from hospital discharge summaries, consultant reports, autopsy reports) in order to perform an independent medical assessment of the reported case.

5.6 ADVERSE EVENTS THAT OCCUR AFTER THE ADVERSE EVENT REPORTING PERIOD

After the end of the adverse event reporting period (defined as 30 days after the last dose of study drug for all AEs and 90 days for serious adverse events and adverse events of special interest), all deaths, regardless of cause, should be reported through use of the Long-Term Survival Follow-Up eCRF.

In addition, if the investigator becomes aware of a serious adverse event that is believed to be related to prior exposure to study drug, the event should be reported through use of the Adverse Event eCRF. However, if the EDC system is not available, the investigator should report these events directly to the Sponsor or its designee, either by faxing or by scanning and emailing the paper Clinical Trial Serious Adverse Event/Adverse Event of Special Interest Reporting Form using the fax number or email address provided to investigators.

5.7 EXPEDITED REPORTING TO HEALTH AUTHORITIES, INVESTIGATORS, INSTITUTIONAL REVIEW BOARDS, AND ETHICS COMMITTEES

The Sponsor will promptly evaluate all serious adverse events and adverse events of special interest against cumulative product experience to identify and expeditiously communicate possible new safety findings to investigators, IRBs, ECs, and applicable health authorities based on applicable legislation.

To determine reporting requirements for single adverse event cases, the Sponsor will assess the expectedness of these events using the following reference document:

- **Atezolizumab Investigator's Brochure**

The Sponsor will compare the severity of each event and the cumulative event frequency reported for the study with the severity and frequency reported in the applicable reference document.

Reporting requirements will also be based on the investigator's assessment of causality and seriousness, with allowance for upgrading by the Sponsor as needed.

An IDMC will monitor the incidence of the above-listed anticipated events during the study. An aggregate report of any clinically relevant imbalances that do not favor the test product will be submitted to health authorities.

6. STATISTICAL CONSIDERATIONS AND ANALYSIS PLAN

This is an open-label, single-arm safety study.

Analysis populations

This study will include the following analysis populations:

- Safety population: The primary analysis population for this study will include all enrolled patients who have received at least one dose of atezolizumab. The safety population will be used for all baseline and safety analyses, unless otherwise stated
- Intent-to-treat population: The intent-to-treat (ITT) population will include all enrolled patients

A per-protocol population will not be defined for this study. However all major deviations (at study entry and on study) will be summarized and reported.

6.1 DETERMINATION OF SAMPLE SIZE

No formal sample size calculation linked to hypothesis testing is done for this descriptive study. The sample size considerations are based upon estimation precision for the incidence of AEs. With 600 patients, the following 95% CIs ([Table 12](#)) could be provided for the different incidences of AEs, which is deemed appropriate for the purposes of the study.

Table 12 Adverse Event Incidence and Corresponding 95% Confidence Intervals

Sample Size	AE Incidence	95% Clopper-Pearson Exact CI
600 patients	1%	1% [0.2% ; 1.8%]
	2%	2% [0.9% ; 3.1%]
	3%	3% [1.6% ; 4.4%]
	5%	5% [3.3% ; 6.7%]
	10%	10% [7.6% ; 12.4%]

CI, confidence interval.

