6.4 PRIMARY ENDPOINT ANALYSIS

All safety analyses will be run on the Safety Analysis set, defined as all enrolled patients who had at least one administration of atezolizumab. The primary analysis will occur approximately 6 months after the last patient has been enrolled.

The incidence of SAEs related to atezolizumab and the incidence of irAEs related to atezolizumab will be summarized by incidence rates and 95% Pearson-Clopper confidence intervals.

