3.5.2 Primary Safety Endpoints

The primary endpoints are the following AE categories:

- Serious AE related to study drug
- Immune-related AE related to study drug

Incidence rates will be provided along with the corresponding 95% Pearson-Clopper CIs. Additionally, both categories will be summarized by SOC, PT and NCI CTCAE grade.

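### The precision table that alone supports 600 patients is labelled exact Clopper-Pearson but contains Wald intervals: all ten limits are wrong, and every upper limit is too low

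*Protocol*

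**What the plan says.** Protocol section 6.1 makes no power calculation: "No formal sample size calculation linked to hypothesis testing is done for this descriptive study". It continues: "The sample size considerations are based upon estimation precision for the incidence of AEs". Table 12 then gives, for 600 patients, a 95% interval at each of five incidences, in a column headed "95% Clopper-Pearson Exact CI":

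| Incidence | Printed interval |
|---|---|
| 1% | 0.2% to 1.8% |
| 2% | 0.9% to 3.1% |
| 3% | 1.6% to 4.4% |
| 5% | 3.3% to 6.7% |
| 10% | 7.6% to 12.4% |

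The section concludes that this precision suits the study. The same ten limits under the same header appear in the protocol synopsis (Statistical Methods, Table 2), in SAP section 2.3 (Table 1), and in the version 3 synopsis reproduced as SAP Appendix 1 (Table 2).

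The primary analysis uses the method that the header names. Protocol section 6.4 has the two primary endpoints "summarized by incidence rates and 95% Pearson-Clopper confidence intervals", and SAP section 3.5.2 says the same: "Incidence rates will be provided along with the corresponding 95% Pearson-Clopper CIs".

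**The concern.** Every printed row is symmetric: 1% ± 0.8, 2% ± 1.1, 3% ± 1.4, 5% ± 1.7, 10% ± 2.4. An exact binomial interval at incidences this far below 50% is not symmetric. It reaches further above the estimate than below it. The symmetry therefore suggests that a normal approximation was used under an exact label.

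With no hypothesis test, this table is the whole quantitative case for the sample size. If its figures do not come from the named method, the judgement that the precision is adequate was made on intervals that the planned analysis will not produce. In a safety study the upper limit matters most, because it says how common an event could still be. That is the limit printed too low.

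**Working it through.** **Inputs.** n = 600, the five incidences, the 95% level and the method name all come from protocol section 6.1 and Table 12. The incidences are whole numbers of events: x = 6, 12, 18, 30 and 60. Rounding of x therefore cannot explain a difference.

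**Step 1: reproduce the printed figures.** The Wald interval is p ± 1.96·√(p(1−p)/n). For 1%: √(0.01 × 0.99 / 600) = 0.00406; times 1.96 = 0.00796; limits 0.204% and 1.796%, which print as 0.2% and 1.8%. The other rows follow in the same way (table below). All ten printed limits are reproduced.

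**Step 2: apply the method named in the header.** The two-sided 95% Clopper-Pearson limits are beta quantiles:

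- lower = Beta(0.025; x, n − x + 1)
- upper = Beta(0.975; x + 1, n − x)

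| Incidence (events) | Printed, % | Wald, % | Clopper-Pearson, % | Exact to 1 decimal, % |
|---|---|---|---|---|
| 1% (6) | 0.2 to 1.8 | 0.204 to 1.796 | 0.368 to 2.164 | 0.4 to 2.2 |
| 2% (12) | 0.9 to 3.1 | 0.880 to 3.120 | 1.038 to 3.468 | 1.0 to 3.5 |
| 3% (18) | 1.6 to 4.4 | 1.635 to 4.365 | 1.787 to 4.700 | 1.8 to 4.7 |
| 5% (30) | 3.3 to 6.7 | 3.256 to 6.744 | 3.399 to 7.061 | 3.4 to 7.1 |
| 10% (60) | 7.6 to 12.4 | 7.600 to 12.400 | 7.718 to 12.684 | 7.7 to 12.7 |

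None of the ten printed limits equals the exact limit at one decimal.

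**Step 3: look for another explanation.** The Wald interval with continuity correction, the Wilson interval, the Jeffreys interval and a 90% Clopper-Pearson interval were also computed. None reproduces the table. Only the plain Wald interval does.

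**Step 4: size of the error.** At one decimal, the exact upper limits exceed the printed ones by 0.4, 0.4, 0.3, 0.4 and 0.3 points, in row order. The exact lower limits exceed the printed ones by 0.2, 0.1, 0.2, 0.1 and 0.1 points. In relative terms the upper limit is 20% higher at 1% incidence (2.164 / 1.8 = 1.20) and 2% higher at 10% (12.684 / 12.4 = 1.02).

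| Incidence | Full width, Wald | Full width, exact | Difference (points) |
|---|---|---|---|
| 1% | 1.59 | 1.80 | 0.20 |
| 2% | 2.24 | 2.43 | 0.19 |
| 3% | 2.73 | 2.91 | 0.18 |
| 5% | 3.49 | 3.66 | 0.18 |
| 10% | 4.80 | 4.97 | 0.17 |

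Differences are taken from the unrounded widths.

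**The case against.** The error is a matter of documentation. No stopping rule, decision rule or power statement uses the table, and the reported intervals will be exact whatever Table 12 says, because protocol section 6.4 and SAP section 3.5.2 specify the method correctly. If precision means width, little is lost: half-widths grow by only 0.08 to 0.10 points. Most of the shift in the upper limit arises because the exact interval sits higher, and the printed lower limits err in the opposite, pessimistic direction. The 20% figure belongs to the worst row. The plan sets no maximum width and no bound to exclude, so nothing shows that the exact limits would have led to a different N. The slip might also lie in the header and not in the numbers.

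All of this stands as a limit on the consequences. It does not remove the error. The table is the only quantitative basis offered for N, its header names one method and its figures come from another, and nothing elsewhere in the documents corrects it. Relabelling would make the table true, but it would then describe an interval that the primary analysis does not use.

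**Conclusion.** The point holds. Table 12 and its three copies carry Wald limits under a Clopper-Pearson header. All ten limits are wrong at the printed precision, and every upper limit is understated, by 0.3 to 0.4 points. The effect is modest: intervals about 0.17 to 0.20 points wider, no bias in any reported result, and no reason in this finding to change N. It should still be corrected, because the sample-size rationale consists of these numbers and they differ from what the primary analysis would give at the same observed rates.

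The figures assume a denominator of exactly 600, as in the plan's table. The primary analysis counts only treated patients, so a somewhat smaller denominator would widen the exact intervals slightly.

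**What to change.** Replace the limits in the protocol synopsis (Table 2), protocol section 6.1 (Table 12) and SAP section 2.3 (Table 1) with the exact values: 1% [0.4; 2.2], 2% [1.0; 3.5], 3% [1.8; 4.7], 5% [3.4; 7.1], 10% [7.7; 12.7]. Correcting the protocol alone is not enough, because section 3 of the SAP gives its analyses precedence over the protocol's and the SAP repeats the table. SAP Appendix 1 reproduces a version 3 synopsis, so a note there is sufficient. Keep N = 600 and add a sentence confirming that the exact precision is acceptable.

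Relabelling the column as a normal approximation is a valid but weaker alternative, since the table would no longer match the primary analysis. Either way the cost is a text correction. With replacement, the stated precision becomes slightly less favourable at the upper limit, while the lower limits rise by 0.1 to 0.2 points.

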6.2 ANALYSIS OF THE CONDUCT OF THE STUDY

Enrollment (e.g., by country, by site), screening failures, study treatment administration, and discontinuation (including reasons) from the study will be summarized using descriptive statistics.

6.3 SUMMARIES OF TREATMENT GROUP

Demographic and other baseline characteristics (at patient and disease level), medical history, prior treatments (study and non-study condition related) will be presented descriptively using the overall safety population. These may also be presented using the ITT population if the difference is more than 5 patients compared with the number of patients in the safety population.

6.4 PRIMARY ENDPOINT ANALYSIS

All safety analyses will be run on the Safety Analysis set, defined as all enrolled patients who had at least one administration of atezolizumab. The primary analysis will occur approximately 6 months after the last patient has been enrolled.

The incidence of SAEs related to atezolizumab and the incidence of irAEs related to atezolizumab will be summarized by incidence rates and 95% Pearson-Clopper confidence intervals.

6.5 MAIN SECONDARY ENDPOINT ANALYSES

6.5.1 Landmark Analysis

Estimates of OS rates at 24 and 36 months in the ITT population will be provided using the Kaplan-Meier methodology, along with 95% CIs calculated using Greenwood's formula.

6.6 OTHER SECONDARY ENDPOINT ANALYSES

6.6.1 Other Safety Analyses

Safety analyses include the following:

- All causality AEs
- All causality AEs (Grades 3–5)
- All causality SAEs
- AEs and SAEs leading to atezolizumab interruption or discontinuation
- AESIs
- irAEs
- Causes of deaths
- Changes from baseline in vital signs during and following atezolizumab administration
- Changes from baseline in clinical laboratory results during and following atezolizumab administration
- Concomitant medications

AEs will be displayed in standard frequency tables according to overall frequency and severity. Time to first incidence of AEs, SAEs, AEs (Grades 3–5) and irAEs will be estimated using the Kaplan-Meier approach. AEs and laboratory parameters will be assessed by the investigator according to the National Cancer Institute Common Terminology Criteria, Version 4.0 (NCI CTC v4.0). AEs and/or SAEs will be coded and analyzed by “preferred terms” according to the Medical Dictionary for Regulatory Activities (MedDRA) and evaluated descriptively

6.6.2 Other Efficacy Analyses

Overall Survival

OS is defined as the time from initiation of study treatment to death from any cause. Data for patients who are not reported as having died at the time of analysis will be censored at the date they were last known to be alive. Patients who do not have post-baseline information will be censored at the date of initiation of study treatment plus 1 day.

Progression-Free Survival

PFS is defined as the time (in months) between the date of initiation of study treatment and the date of first documented disease progression or death, whichever occurs first. PFS will be calculated based on disease status evaluated by the investigator according to RECIST v1.1 and also by disease status according to modified RECIST. Patients who are alive and have not experienced disease progression at the time of analysis will be censored at the time of the last tumor assessment. Patients with no post-baseline tumor assessment will be censored at the time of initiation of study treatment plus 1 day.

Objective Response Rate

Objective response is defined as a confirmed complete or a partial response per RECIST v1.1 and/or modified RECIST. Patients without any post-baseline tumor assessments will be considered non-responders. An estimate of ORR will be provided along with the corresponding 95% CIs calculated using the Clopper-Pearson method.

Duration of Response

For patients who have experienced an objective response (CR or PR) during the study as assessed by the investigator, DOR is defined as the duration from the first tumor assessment that supports the patient's objective response (CR or PR, whichever is first recorded) to disease progression or death due to any cause, whichever occurs first. Patients who are alive and who have not experienced disease progression at the time of analysis will be censored at the time of the last tumor assessment date. If no tumor assessments were performed after the date of the first occurrence of a complete or partial response, DOR will be censored at the date of the first occurrence of a complete or partial response plus 1 day. Two separate analyses will be presented for RECIST v1.1 and modified RECIST.

6.6.3 Exploratory Efficacy Analysis

The following efficacy endpoints will be evaluated to further assess the efficacy of atezolizumab after disease progression (no confirmation of response will be required for these analyses)

In those patients who received further anti-cancer therapy:

- Progression-free survival from start of new anti-cancer therapy, defined as the time from initiation of new anti-cancer therapy to objective tumor progression on next-line treatment or death from any cause
- Objective response rate from start of new anti-cancer therapy, defined as the percentage of patients who attain complete response (CR) or partial response (PR)

In the ITT population:

- Progression-free survival 2 (PFS2), defined as the time from initiation of study treatment to objective tumor progression on next-line treatment or death from any cause

The prior analyses might be repeated in the following subgroups, if enough patients are available:

- Presence of CNS metastases at baseline (yes vs. no)
- ECOG performance status (0 or 1 vs. 2)
- Histologic subtype (squamous vs. non-squamous)
- History of or current autoimmune disease (yes vs. no)
- Prior anticancer treatment

